9.9.2.1 Secondary Efficacy Analyses at Secondary Endpoints

Assess 3 vs. 2 experimental MDMA sessions

For the CAPS, the absolute changes in the measure from the primary endpoint to end of Stage 1 for the 100 and 125 mg groups will be compared with t-tests. In the crossover subjects (40 mg) the absolute changes in the measures from the secondary (visit 27) endpoint to end of Stage 2 (visit 32) will be compared with t-tests.

Crossover Subject Analyses

CAPS data from subjects assigned to the 40 mg group in Stage 1, i.e. ‘crossover population,’ will be analyzed by t-tests on difference scores from primary endpoint (visit 12) in Stage 1 to secondary endpoint in Stage 2 (visit 27). Additionally, the following measures’ total scores will be analyzed in this same fashion: CAPS, PTGI, BDI-II, GAF, PSQI, DES-II, PDS.

Long-term Follow-up

For the CAPS, PDS, PTGI, BDI-II, GAF, PSQI, and DES-II, the absolute changes in the measures from baseline to the long-term follow-up visit (one year post final experimental year) will be compared with t-tests. The absolute changes in the measures from long-term follow-up to End of Stage 1 (visit 17, 100 mg and 125 mg) or long-term follow-up compared to End of Stage 2 (visit 32, 40 mg) will be compared with t-tests.

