that the therapeutic benefits have been sustained over time on average, although two subjects experienced a relapse in PTSD symptoms [2]. The sponsor also supported a randomized, double-blind pilot study in 12 subjects with chronic, treatment-resistant PTSD in Switzerland with three experimental sessions. The study results suggested a trend toward significant improvement in subjects receiving full dose MDMA, when compared to 25 mg active placebo MDMA at two-month follow-up. The improvement continued to increase during the 12-month follow-up [3]. In addition, the sponsor supported an initial pilot study with two experimental sessions comparing full dose to 25 mg active placebo MDMA in Israel that enrolled five subjects, with no drug-related Serious Adverse Events (SAEs). Subjects reported benefits that were not reflected in CAPS scores, leading to termination of the study for additional training of the Israeli therapists and research team. Most recently, in the U.S., MAPS has commenced a follow-up to its initial U.S. trial with a PTSD relapse study, along with a second Phase 2 trial, specifically treating U.S. military veterans.

As of March 2014, MDMA has been administered to more than 960 research subjects, in both Phase 1 and Phase 2 studies, without any occurrences of unexpected drug-related SAEs [1, 3, 47, 68, 72-95].

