4.2 Secondary Objectives

The following objectives will compare each active dose group and the comparator dose group in Stage 1:

- Assess changes in self-reported PTSD symptoms as measured with the PTSD Diagnostic Scale (PDS) at baseline, after each experimental session and/or the primary endpoint.
- Assess depression symptoms with the Beck Depression Inventory-II (BDI-II) at baseline and the primary endpoint.
- Assess global functioning with the Global Assessment of Functionality (GAF) at baseline and the primary endpoint.
- Assess self-reported sleep quality with the Pittsburgh Sleep Quality Index (PSQI) at baseline and the primary endpoint.
- Assess self-reported dissociation symptoms with the Dissociative Experiences Scale II (DES-II) at baseline and the primary endpoint.
- Assess self-reported posttraumatic growth with the Posttraumatic Growth Inventory (PTGI) at baseline and the primary endpoint.

The following objectives will compare effects in specified subjects:

- Assess PTSD symptoms via CAPS and PDS, depression symptoms via BDI-II, global functioning via GAF, sleep quality via PSQI, posttraumatic growth via PTGI, and dissociation symptoms via the DES-II, throughout Stage 2 in comparison to Stage 1 in crossover subjects.
- Assess long-term effects of MDMA-assisted psychotherapy on symptoms of PTSD, depression, and global function, sleep quality, dissociation symptoms via CAPS and PDS, BDI-II, GAF, PSQI, PTGI (in reference to start of the study), and DES-II one year after the final experimental session for each subject.

The following objectives will include exploratory analyses intended to inform future protocol design:

- Explore the effects of each experimental session upon self-reported changes in consciousness, as those associated with a transformational or mystical experience via the States of Consciousness Questionnaire (SOCQ).
- Assess the effect of the third experimental session for active dose subjects in Stage 1 and Stage 2 using CAPS, PDS, BDI-II, GAF, PSQI, PTGI (in reference to start of the study), and DES-II.
- Assess the ability of the investigators and subjects to accurately guess treatment group assignment in Stage 1.
- Correlate adherence to the treatment manual with Global CAPS scores using adherence criteria ratings to assess videos of psychotherapy sessions.

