6.0 Randomization and Blinding

Per Amendment 6, 26 subjects will be enrolled into the study. The randomized portion of the study will be blinded and there will be a 12:9:5 ratio between subjects in the active dose 1, active dose 2, and comparator dose treatment groups. Subjects will be assigned subject numbers, and subjects will be randomized in a blinded fashion.

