9.0 Analyses

In general, nominal variables will be described in terms of frequencies and percentages and analyzed using chi square analysis. Ordinal and non-normal continuous variables will be described using sample median and range, and analyzed by non-parametric statistical tests, and approximately normal variables will be described using sample mean and standard deviations and analyzed by parametric statistical tests. All statistical tests will be two-sided and a difference resulting in a p-value of less than or equal to 0.05 will be considered statistically significant. All p-values will be rounded to and displayed in four decimals. If a p-value less than 0.0001 occurs it will be shown in tables as <0.0001. For any analysis that is called out as parametric, e.g. t-test, the parametric assumptions will be examined. If necessary, nonparametric analyses will be utilized, e.g. Wilcoxon rank-sum test.

Clinical data will be presented in tabular format. Data not subject to analysis according to this plan will not appear in any tables or graphs, but will be included in the data listings. Analyses will be carried out with SAS Version 9.3 or higher. Selected results may be presented graphically using standard graphical software.

Post-hoc exploratory analyses not identified in this SAP may be performed to further examine the study data. These analyses will be clearly identified as such in the final clinical study report.

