9.1 Analysis Populations

Modified Intent-to-treat (mITT): all subjects who were randomized, received at least one experimental session and completed at least one outcome assessment

Per protocol (PP): all subjects who completed two experimental sessions and primary outcome assessment in Stage 1 and did not experience a major protocol deviation

Crossover: all subjects who completed Stage 2 in addition to completing Stage 1

Safety: all subjects who receive any study treatment

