9.9.1 Primary Efficacy Analyses

Clinician Administered PTSD Scale-4 (CAPS-4)

The primary efficacy evaluation is the change from baseline to the primary outcome timepoint (visit 12) in the CAPS-4 Global Severity score of PTSD (difference score). The primary efficacy comparison will be made with ANOVA at an alpha level of 0.05. If the primary hypothesis rejects, pairwise comparisons among the treatment groups will be made with t-tests. If the parametric assumptions for the ANOVA and t-test analyses are not met, the analogous nonparametric methods will be used (Kruskall-Wallis, Wilcoxon Rank-Sum).

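### The crossover t-test measures change within Stage 2 only; it does not set that change against the same subjects' Stage 1 change, so equal improvement in both stages could still give a significant result

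*SAP*

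**What the plan says.** The objective, worded alike in Protocol 3.2 and SAP 4.2, is to assess CAPS, PDS, BDI-II, GAF, PSQI, PTGI and DES-II "throughout Stage 2 in comparison to Stage 1 in crossover subjects". It does not say whether levels or changes are to be compared.

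The analysis is in SAP 9.9.2.1, under secondary efficacy analyses. CAPS in the 40 mg subjects "will be analyzed by t-tests on difference scores from primary endpoint (visit 12) in Stage 1 to secondary endpoint in Stage 2 (visit 27"), and "the following measures’ total scores will be analyzed in this same fashion: CAPS, PTGI, BDI-II, GAF, PSQI, DES-II, PDS". SAP 9.0 sets the criterion: "All statistical tests will be two-sided and a difference resulting in a p-value of less than or equal to 0.05 will be considered statistically significant". The population is defined in SAP 9.1: "Crossover: all subjects who completed Stage 2 in addition to completing Stage 1". Protocol 12.0 describes only an exploratory within-subject analysis of crossover subjects in Stage 2, together with effect sizes for each stage.

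The Stage 1 change, "change from baseline to the primary outcome timepoint (visit 12) in the CAPS-4 Global Severity score of PTSD (difference score"), is used in SAP 9.9.1 for the comparison between randomised groups. Protocol 5.2.9 makes the visit 12 scores the Stage 2 baseline, unless more than eight weeks pass before visit 18, in which case the measures are repeated and the new scores are used.

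**The concern.** The two stages are close to matched up to the endpoints being compared. By Tables 2 and 3 and Protocol 5.2.9, each has two drug sessions, three integrative sessions after each of them, and an outcome visit a month after the second. Stage 2 differs in having one preparatory visit instead of three, in open-label dosing and in dose. The comparison that this layout invites is the Stage 2 change against the Stage 1 change in the same people.

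The planned test leaves out the second half of that comparison. Every subject has 40 mg first and an active dose second, so a fall from visit 12 to visit 27 is what an added effect of the active dose would produce. It is also what a continuation of the Stage 1 improvement would produce. Continued improvement is plausible on the protocol's own account: of an earlier sponsor study, Protocol 2.2.3 reports that "The improvement continued to increase during the 12-month follow-up". That sentence follows on from a result in full-dose subjects, so it shows only that improvement can continue, not what follows 40 mg.

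At stake is how a significant result is read. Without the Stage 1 change beside it, a reader may take it as the active dose working where the comparator dose did not.

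**Working it through.** **What the test contains.** Write B for baseline, and V12 and V27 for the two endpoint scores. The planned statistic is a one-sample t on V27 − V12, with the null hypothesis that its mean is zero. As V12 is normally the Stage 2 baseline, this is the change over the first two Stage 2 sessions. Equivalently, it is the Stage 2 endpoint level minus the Stage 1 endpoint level, in a fixed order.

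**Whether another test fills the gap.** The other tests on these subjects' outcome scores in SAP 9.9.2.1 are V27 to visit 32, baseline to long-term follow-up, and visit 32 to long-term follow-up. None uses V12 − B in the same subjects as a comparator.

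**The plan's own figure.** The only power calculation is in Protocol 12.1: 18 versus 5 subjects, effect size 0.8, power 0.33. The noncentrality is 0.8 × √(18×5/23) = 1.583, with 21 degrees of freedom and a two-sided critical value of 2.080. Power is 0.327, so the figure reproduces. For an effect size of 1.1 the result is 0.546. The protocol prints 0.55 there as an effect size, but it is evidently power. No power is given for the crossover analysis.

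**Inputs for the crossover test.**
- n = 5 planned in the comparator arm (SAP 6.0: "there will be a 12:9:5 ratio between subjects in the active dose 1, active dose 2, and comparator dose treatment groups"). Only Stage 2 completers count, and the arm of the replaced subjects is not stated, so n = 3 to 7 is also shown.
- Two-sided 0.05 (SAP 9.0).
- The SD of change and the correlations between visits are not in the documents. Results are in SD units, or use an assumed SD of 20.

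**Probability that the planned test is significant when both stages improve equally.** Let d be the common mean change divided by the SD of the change. The noncentrality is d√n on n − 1 degrees of freedom; for n = 5 the critical value is 2.776.

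| d | d√5 | P(significant), n = 5 |
|---|---|---|
| 0 | 0 | 0.05 |
| 0.75 | 1.677 | 0.25 |
| 1.0 | 2.236 | 0.40 |
| 1.5 | 3.354 | 0.71 |

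At d = 1.0 the figure runs from 0.18 (n = 3) to 0.60 (n = 7). With an assumed SD of 20, the three non-zero rows are common changes of 15, 20 and 30 CAPS points. For a 20-point change, SDs from 15 to 30 give 0.61 down to 0.21.

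**The paired contrast.** D = (V27 − V12) − (V12 − B). If both stages improve equally, D has mean zero. In 200,000 simulated trials with n = 5, correlations between visits of 0.3, 0.5 and 0.7, and an equal improvement of 0.8 SD of the raw score in each stage, the planned test rejected in 22%, 28% and 42%. With 1.1 SD it rejected in 36%, 47% and 67%. A t-test on D rejected in about 5% in every case.

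**Precision of the contrast.** With SD 20 for each change and correlation r between the two changes, SD(D) = 20√(2(1 − r)). The expected 95% half-width is 2.776 × 0.940 × SD(D)/√5, where 0.940 is the expected ratio of sample SD to true SD at n = 5.

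| r | SD(D) | Half-width, CAPS points | Power for a 20-point excess in Stage 2 |
|---|---|---|---|
| 0.3 | 23.7 | 27.6 | 0.31 |
| 0 | 28.3 | 33.0 | 0.23 |
| −0.3 | 32.2 | 37.6 | 0.19 |
| −0.5 | 34.6 | 40.4 | 0.17 |

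The last row is the relevant one if the three visits have equal variances and equal correlations. V12 then enters the two changes with opposite signs, and their correlation is exactly −0.5.

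**The case against.** Four objections have force.

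First, a reader might infer that the test cannot answer the stated objective. The documents do not support that. The objective speaks of assessing symptoms in Stage 2 in comparison with Stage 1, and V27 against V12 is literally a comparison of the two stage endpoints within subject. The objective is ambiguous between levels and changes. The weakness lies in what a difference in levels can show when the order is fixed.

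Second, a reader might infer that the plan would declare an active-dose effect from this test. No section attaches that conclusion. Stage 2 is described throughout as open-label and exploratory as to dose, and the randomised dose comparison is the Stage 1 analysis. The SAP does place the crossover test among its secondary efficacy analyses, so misreading is a foreseeable risk, but it is not a stated plan.

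Third, the 25% to 71% is not a type I error rate. It is the test's power against a real change in Stage 2; the test's own null hypothesis is no change, and there it keeps 5%. The inputs are also assumed. At SD 20 the upper end needs a 60-point fall over two stages, which a subject entering at the minimum CAPS of 50 (Protocol 4.2.1) cannot have.

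Fourth, the contrast is a poor replacement as a test. It has low power at n = 5. Regression to the mean after the CAPS entry threshold can enlarge the Stage 1 change, and a floor can limit the Stage 2 change; both push against Stage 2. The 5% rejection rate shown for it assumes that neither operates. The study is also declared an underpowered pilot, and the stage-wise effect sizes in Protocol 12.0 would allow a rough side-by-side view.

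All four limit the conclusion and the fix. None puts the Stage 1 change into the analysis.

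**Conclusion.** The point holds in a limited form. For all seven measures, the planned crossover test is a test of change within Stage 2. It cannot separate a larger response in Stage 2 from the same improvement continuing, and nothing else planned tests that difference. Equal improvement in both stages could be significant in roughly 25% to 71% of trials at n = 5, for common changes of 0.75 to 1.5 SDs of the change score. That the planned test lacks the Stage 1 change follows from the text alone. The percentages rest on normal data and on assumed effect sizes, because the documents give no SD of change.

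This warrants a correction to labelling and an added estimate. It does not warrant removing the planned analysis or making the contrast a confirmatory test.

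**What to change.** In SAP 9.9.2.1:

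1. Keep the visit 12 to visit 27 analysis, and label it a within-Stage-2 change that is not evidence of active dose over 40 mg.
2. Add the paired contrast (V27 − Stage 2 baseline) − (V12 − Stage 1 baseline) for CAPS, PDS, BDI-II, GAF, PSQI and DES-II, as an estimate with a 95% CI and not as a confirmatory test. Use the re-measured Stage 2 baseline where Protocol 5.2.9 requires one; the SAP currently fixes visit 12 in all cases. Omit PTGI, because by Protocol 5.1.1 its baseline refers to the time since the trauma and its later scores to the start of the study.
3. State that the contrast does not isolate dose: the order is fixed, Stage 2 is open-label, effects may carry over from Stage 1, baseline is subject to regression to the mean from the entry threshold, floor effects are possible, visit 12 enters both changes, and only Stage 2 completers are included.
4. In SAP 4.2, say whether the objective concerns levels, changes or both.

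The cost is a few lines of text, with no new data. The downside is precision: with about 5 subjects the interval will reach about 28 to 40 CAPS points either side if the SD of change is 20, so it will seldom settle the question. It will show how little the crossover data can say about dose.

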4.1 Planned Duration of Study and Visit Windows

Subjects enrolled in this study will fall into two categories that will determine the duration of the study. These include the follow-up portion of the study, which encompasses 12 months after the final experimental session.

- Active dose subjects completing Stage 1 only: 15 months.
- Comparator dose subjects who continue and complete Stage 2: 18 months.

Screening may take up to two months, with the baseline CAPS being conducted no more than 8 weeks before the first experimental session, leaving room for appropriate medication washout of at least five half-lives of pre-study psychiatric medications and active metabolites, and one additional week for stabilization. For example, the maximum washout would be seven weeks for subjects tapering off of fluoxetine plus one week for stabilization. Preparatory sessions should be scheduled approximately one week apart, with the first experimental session taking place three to five weeks after enrollment, and at most 8 weeks after the baseline CAPS. The maximum window from the start of screening to the first experimental session is 13 weeks. The optimal timing for Stage 2 is one month after the primary endpoint visit in Stage 1, with a maximum allowable window of five months. Any delay between visits would result in a corresponding extension of study duration.

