5.2.9 Open-label Stage 2 (Comparator Dose Subjects from Stage 1)

During Stage 2:

- a. Subjects will be reminded that participation in Stage 2 is voluntary and optional.
- b. Subjects who elect to cross over to Stage 2 will undergo the same course of therapy and evaluation as in Stage 1, with the exception that the subject will complete a single preparatory psychotherapy session instead of three (see Section 5.2.2), and varied active doses of MDMA will be administered in an open-label context to explore the optimal therapeutic dose (e.g. without unblinding). Visits will be scheduled consecutively according to the Time and Events Table.
- c. Assessment of PTSD symptoms at the primary endpoint will serve as baseline assessments in Stage 2.
- d. If the start of Stage 2 is delayed for more than eight weeks from the primary endpoint (Visit 12) to the first preparatory session in Stage 2 (Visit 18), the IR will re-administer the CAPS and GAF. The subjects will complete the PDS, BDI-II, PSQI, PTGI (in reference to start of the study), and the DES-II. These scores will be used as the baseline for comparison to assessment at the secondary endpoint and the end of Stage 2.
- e. Experimental sessions will be conducted according to procedures described in Section 5.2.3.
 - 1. During the first experimental session, subjects will receive a 100 mg initial dose of MDMA and may receive a 50 mg optional supplemental dose of MDMA.
 - 2. At the beginning of each of the second and third experimental sessions, the co-therapists, in consultation with the subject, will decide whether to administer an initial dose of 100 mg or 125 mg initial dose of MDMA. If a 100 mg initial dose of MDMA is selected, an optional supplemental dose of 50 mg MDMA may be administered. If a 125 mg initial dose of MDMA is selected, an optional supplemental dose of 62.5 mg MDMA may be administered.
 - 3. If the PI decides not to administer the optional supplemental dose and/or the optional clinical titration dose in a given experimental session, the unused capsules will be kept in their respective inner envelopes inside of the primary container in the safe.
- f. Integrative sessions will be conducted according to procedures described in Sections 5.2.4 and 5.2.6.
- g. Phone calls will be conducted according to procedures described in Section 5.2.5.

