SUD		✓ ^{D,E}		✓ ^{D,E}			✓ ^{D,E}			
Overnight Stay, SOCQ		✓		✓			✓			
Integrative Therapy Session			✓ ^A		✓ ^A			✓ ^A		
Seven Days Telephone Contact			✓		✓			✓		
AEs Requiring Medical Attention	✓	✓	✓	✓	✓	✓	✓	✓	✓	
Spont. Reported Reactions and all AEs		✓	✓ ^F	✓	✓ ^F	✓	✓	✓ ^F	✓	
Changes in Tinnitus and/or Pain		✓ ^{J,D}	✓ ^{J,D}	✓ ^{J,D}	✓ ^{J,D}	✓ ^J	✓ ^{J,D}	✓ ^{J,D}	✓ ^J	✓ ^J
AEs of psychiatric status or withdrawal	✓	✓	✓	✓	✓	✓	✓	✓	✓	✓
Serious Adverse Events	✓	✓	✓	✓	✓	✓	✓	✓	✓	✓
Perception of Experimental Sessions						✓			✓	
Complete Stage 2 go to follow-up									✓	
RRPQ									✓	
Issue Memory Aid Card									✓	
Follow-up Questionnaire										✓
Termination Visit										✓

* If Visit 18 is more than 8 weeks after Visit 12, then subjects will need to repeat measures prior to starting Stage 2.

A = First session is one day after experimental session; B = Approximately six hours post MDMA; C = At the beginning of the session; D = As needed; E = Approximately every 60 minutes; F = Reactions collected for seven days post experimental session; G = All visits and Day 2 and Day 7 phone calls only; H = One month after the second experimental session but before the third experimental session; I = On the day of the third integrative session; J = Only in subjects with pre-existing tinnitus and/or chronic pain.

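### The SAP's crossover analysis does not carry over the protocol's baseline rule for subjects who start Stage 2 more than eight weeks after Visit 12

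*SAP*

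**What the plan says.** **The analysis.** SAP 9.9.2.1, under Crossover Subject Analyses, states that CAPS data from the 40 mg group "will be analyzed by t-tests on difference scores from primary endpoint (visit 12) in Stage 1 to secondary endpoint in Stage 2 (visit 27"). It then extends the method to the other scales: "the following measures’ total scores will be analyzed in this same fashion: CAPS, PTGI, BDI-II, GAF, PSQI, DES-II, PDS". It gives no alternative starting assessment. SAP 9.5 takes baseline values from the screening/baseline visit (with a separate rule for the C-SSRS) and defines no Stage 2 baseline.

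**The protocol's baseline rule.** Protocol 5.2.9(c) gives the default: "Assessment of PTSD symptoms at the primary endpoint will serve as baseline assessments in Stage 2". Item (d) gives the exception. It opens with "If the start of Stage 2 is delayed for more than eight weeks from the primary endpoint (Visit 12"), counted to the Stage 2 preparatory session at Visit 18, and lists CAPS, GAF, PDS, BDI-II, PSQI, PTGI and DES-II for repetition. It then says what the repeats are for: "These scores will be used as the baseline for comparison to assessment at the secondary endpoint and the end of Stage 2".

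**The schedule.** The Stage 2 events table in SAP 5.0 points to Visit 12 for these scales, with an asterisk leading to this footnote: "If Visit 18 is more than 8 weeks after Visit 12, then subjects will need to repeat measures prior to starting Stage 2". The footnote does not say how the repeated scores are used. Protocol 4.1 describes a start one month after the primary endpoint visit as optimal, "with a maximum allowable window of five months".

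**The concern.** The comparison in SAP 9.9.2.1 is one for which the protocol specifies the baseline, and it covers the same seven measures. A programmer following the SAP would subtract Visit 12 for every subject. For a delayed subject, that leaves unused an assessment collected to serve as the baseline.

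The choice matters because of what can happen between Visit 12 and a late Stage 2 start. The CAPS covers the last month only (Protocol 5.1.1), so after a long delay Visit 12 describes a period well before the first open-label session. The subject learns the assignment at Visit 12 (Protocol 5.2.7). The comparator dose is itself expected to have some therapeutic effect, though a smaller one (Protocol 2.4), and that effect could fade. Scores could move either way, so starting from Visit 12 cannot be called conservative. Any such movement would be counted as part of the change over the open-label sessions.

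If the baseline is still unsettled at analysis, there are two defensible choices in a very small sample, and the choice could be made after seeing the results.

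**Working it through.** The plan gives no power or precision figure for this comparison, so there is none to reproduce. The check is a comparison of the texts, followed by a scale calculation.

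**1. Do the rules conflict?**
- Visit 18 eight weeks or less after Visit 12: the protocol baseline is Visit 12 and the SAP start point is Visit 12. They agree.
- Visit 18 more than eight weeks after Visit 12: the protocol baseline is the repeat assessment and the SAP start point is still Visit 12. They disagree.

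**2. Can the second case arise within protocol?** The limit is five months: 5 × 52/12 = 21.7 weeks. The trigger is 8 weeks. About 21.7 − 8 = 13.7 weeks of the permitted window lie beyond it, so it can.

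**3. Which analyses are affected?** Only the Visit 12 to Visit 27 difference scores. The primary analysis (SAP 9.9.1) runs from screening baseline to Visit 12. The third-session comparison in crossover subjects runs from Visit 27 to Visit 32. The long-term comparisons use screening baseline or the end-of-stage visit. None of these uses a Stage 2 baseline.

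**4. How large could the effect be?** Inputs:
- n = 5, the planned comparator group (SAP 6.0, ratio 12:9:5). Fewer may cross over.
- x = CAPS change between Visit 12 and the repeat assessment. Not in the documents; assumed 5 to 10 points.
- k = number of delayed subjects. Not in the documents; 0 to 5.
- SD of the change score. Not in the documents; assumed 15 and 25.

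If k subjects each move by x in the same direction, the choice of baseline shifts the mean change by k·x/n:
- k = 0: no shift.
- k = 1: 5/5 = 1 to 10/5 = 2 points. With n below 5, one subject weighs more, which is why x/5 is a minimum.
- k = 5: 5 to 10 points. This is the extreme case.

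The standard error of the mean change is SD/√n:
- SD 15: 15/√5 = 6.7
- SD 25: 25/√5 = 11.2

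Shift in standard errors:

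| Delayed | Shift (points) | SD 15 | SD 25 |
|---|---|---|---|
| 1 of 5 | 1–2 | 0.15–0.30 | 0.09–0.18 |
| 5 of 5 | 5–10 | 0.75–1.5 | 0.45–0.89 |

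**The case against.** **The protocol governs.** SAP 5.0 calls the protocol the definitive reference, and its schedule marks Visit 12 with an asterisk leading to the repeat-measures footnote. On that view, visit 12 in SAP 9.9.2.1 is shorthand that includes the exception. This does not settle the matter. The deference sentence introduces the design overview and sets no baseline for the analysis, and the footnote concerns collection only. If the protocol does govern, the analysis wording still needs correcting.

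**Visit 12 has its own rationale.** A secondary objective compares Stage 2 with Stage 1 in crossover subjects, and Visit 12 is their Stage 1 outcome. This stands. It is a good reason to keep a Visit 12 version, but it does not cancel the protocol's specific rule.

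**The practical effect may be nil.** The schedule places Visit 18 within a month of Visit 12, and neither document reports a delayed subject. Protocol 12.0 calls the Stage 2 within-subject analysis exploratory, and no stated decision depends on it. All of this stands and limits the weight of the point.

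**Stronger readings to avoid.**
- A reader might infer that the crossover estimate is biased. The documents give no drift and no count of delayed subjects, so this cannot be shown.
- A reader might infer that the SAP deliberately discards the repeat scores. It is silent on their use, which is a different matter.
- A reader might take every instrument to be repeated. The protocol lists seven; RBANS and PASAT are not among them.
- A reader might call the interval untreated. Ongoing outside psychotherapy is permitted (Protocol 4.2.1), so *without study drug* is the accurate description.

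The protocol's rule also does not remove all drift, since it accepts up to eight weeks without re-measurement.

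**Conclusion.** SAP 9.9.2.1 is wrong as written for any crossover subject whose Visit 18 is more than eight weeks after Visit 12. It states a start point that contradicts Protocol 5.2.9(d), so this is more than missing detail. For subjects who start within eight weeks, the two documents agree.

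The text mismatch is certain; its numerical effect is not. One delayed subject with an assumed shift of 5 to 10 CAPS points would move a five-subject mean by 1 to 2 points. The larger figures in the table require all five subjects to be delayed and to move the same way, and they depend on the assumed SD. The consequence is confined to one open-label, within-subject secondary comparison in at most five planned subjects. It is worth correcting before analysis because the remedy is cheap and removes a choice that could otherwise be made with the results in view.

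**What to change.** In SAP 9.5, add a definition: the Stage 2 baseline is Visit 12, or the repeat pre-Stage 2 assessment when Visit 18 is more than eight weeks after Visit 12, for CAPS, GAF, PDS, BDI-II, PSQI, PTGI and DES-II.

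In SAP 9.9.2.1, replace Visit 12 as the start of the crossover difference scores with that Stage 2 baseline. Keep the Visit 12 to Visit 27 difference for all crossover subjects as a named sensitivity analysis, because it addresses the Stage 2 versus Stage 1 objective. Report how many subjects used the repeat assessment.

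The cost is SAP wording and one extra sensitivity run. The protocol already requires the repeat scores to be collected.
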